3.2 Study Treatment

3.2.1 Treatment, Dose, and Mode of Administration

AK002 will be administered as an intravenous (IV) infusion at a dose of 0.3 mg/kg on Study Day 1. If well tolerated, the dose will be increased to 1 mg/kg on study Day 29 and Day 57 (± 2 days). Dose will be increased to 3 mg/kg on Days 85, 113 and 141 if the UCT score is < 12 or at the discretion of the Investigator in consultation with the Allakos Medical Monitor and if the 1 mg/kg dose was well tolerated. If the UCT score is ≥ 12 and if the Investigator in consultation with the medical monitor feels that the patient has received adequate symptom improvement, then the patient will continue to receive 1 mg/kg dose. The amount of AK002 to be administered will be calculated based on the patient's body weight determined within 24 hours of each infusion.

Subjects in the CholU, UF, and CSU-XOLAIR® failure cohorts at the select sites will be allowed to participate in the Extended Dosing part of the study if they meet the symptom criteria below: subjects must have a baseline (Day 1) UCT of ≤ 5 and a week 22 (Day 155) UCT of ≥ 12 (Complete Response). They must have a UCT of ≤ 5 between Day 155 and Day 309 (i.e., within 6 months from last dose). All subjects that decide to receive the extended dosing will start with a dose of 0.3 mg/kg, followed by possible dose increases to 1 mg/kg and 3 mg/kg for subsequent infusions. The Investigator in consultation with the Medical Monitor may increase the dose to 6 mg/kg and then to 10 mg/kg if they think that the patient has not received benefit from the lower doses.

3.2.2 Duration of Study

Total subject duration on the main study is approximately 32 weeks.

- Screening phase: 4 weeks
- Treatment phase: 20 weeks
- Follow up after Treatment phase: 8 weeks

For subjects who participate in the Extended Dosing part (select sites) of the study, their total extended duration is up to 52 weeks.

- Screening: 3 weeks
- Treatment phase: up to 44 weeks (12 infusions)
- Follow up phase: 8 weeks

3.3 Methods of Assigning Subjects to Treatment Group

All subjects will receive the same treatments. Approximately 48 subjects who meet all of the inclusion but none of the exclusion criteria will be enrolled and assigned a patient ID number (PID). The PID is comprised of study number (first 3 digits), site number (second 3 digits), disease

cohort (the 7th digit), and order of enrollment (the last 2 digits). The disease cohorts and the approximate sample sizes are defined as follows.

- 1 = Cholinergic Urticaria (CholU) (n=12)
- 2 = Urticaria Factitia (UF) (n=12)
- 3 = Chronic Spontaneous Urticaria Xolair Naïve (CSU-XN) (n=12)
- 4 = Chronic Spontaneous Urticaria Xolair Failure (CSU-XF) (n=12)

3.4 Blinding

Not applicable, as the study is open label.

3.5 Hypotheses

There are no formal tests of hypotheses in this study.

3.6 Determination of Sample Size

The planned sample size of approximately 48 subjects is based on common practice in early phase, proof-of-concept studies.

3.7 Changes to Analyses Planned in the Protocol

None.

3.8 Efficacy Assessments

A number of cohort-specific efficacy variables, including patient-reported outcome (PRO) instrument, will be assessed during the study. Subjects will be administered only with the instruments relevant to their condition (see

Table 3).

Table 3 Patient-Reported Outcome Instruments for Efficacy Assessment

Patient Reported Outcome Instrument	Disease Cohort		
	CholU	UF	CSUs
Urticaria Control Test (UCT) (monthly)	x	x	x
Urticaria Patient Daily Diary (UPDD)			
• [REDACTED]			
• UAS7 (itch and hives)	x	x	x
[REDACTED]			
[REDACTED] *	x	x	x
[REDACTED]	x	x	x

* If applicable. All patients who have a history of [REDACTED] at Screening will complete the [REDACTED] and the [REDACTED]

3.8.1 Urticaria Control Test

The Urticaria Control Test (UCT) ([Appendix B.2](#)) is a 4-item questionnaire for assessing CU disease activity retrospectively over the previous 4 weeks. Each item is rated on a Likert-scale (0 = very often to 4 = not at all) and a total score (the sum of all item scores) is calculated (range, 0 to 16; higher scores indicate better disease control; scores ≥ 12 are consistent with well-controlled disease). The UCT total score will not be calculated when ≥ 1 item within the questionnaire is missing.

CR, CMR, and DC for UCT are defined in Section 4.

3.8.2 [REDACTED]

[REDACTED] ([Appendix B.3](#)) is a questionnaire for the last 2 weeks. It comprises [REDACTED] each that are scored from [REDACTED] relating to overall functioning (including work, physical well-being, leisure and social activities), sleep, itching/embarrassment, mental status, swelling/eating, and limits in look (limitations in choice of clothing or cosmetics used due to [REDACTED]). Total scores range from 0 to 100, with higher scores indicating worse [REDACTED]. The [REDACTED] total score will not be calculated when >14 items within the questionnaire are missing. The [REDACTED] domain scores as well as the total score are calculated by using the following formula:

$$\frac{\sum_{\text{nonmissing items}} \text{Item Score Reported}}{\sum_{\text{nonmissing items}} \text{Max Possible Item Score}} \times 100$$

3.8.3

[REDACTED] (Appendix B.4) is a questionnaire for the last 2 weeks. The total score is calculated from the [REDACTED] scores. Score will be calculated using the formula described in Section 3.8.2.

3.8.4

[REDACTED] (Appendix B.5) is a questionnaire for the last 7 days. It comprises [REDACTED] items. Total score will be calculated and converted to the scale of 0-100 using the formula described in Section 3.8.2.

3.8.5

[REDACTED] (Appendix B.6) is a questionnaire for the last 4 weeks. It comprises [REDACTED] items and will be grouped into [REDACTED] domains. The domain and total scores will be calculated and converted to the scale of 0-100 using the formula described in Section 3.8.2.

3.8.6

[REDACTED] (Protocol Appendix B.7) is a questionnaire for the last 7 days. It is a [REDACTED]-item [REDACTED]-specific health-related quality of life measure. An overall score will be calculated as well as for the following domains: Symptoms and Feelings, Daily Activities, Leisure, Work and School, Personal Relationships, Treatment. The minimally important difference of the overall [REDACTED] score for patients with CSU has been estimated to be [REDACTED]. The total score is the sum of all item scores, ranging from [REDACTED] with higher score for more impairment. The total score will not be calculated if >1 item score is missing.

[figure not shown]

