#### 10.4.3 [REDACTED]

[REDACTED] is the first disease-specific [REDACTED] questionnaire for [REDACTED]. It contains [REDACTED] each that are scored from 0 to 4 and relating to overall functioning (including work, physical, leisure and social activities), sleep, itching/embarrassment, mental status, swelling/eating, and limits

looks (limitations in choice of clothing or cosmetics used due to [REDACTED]). The recall period is 2 weeks. Total scores range from 0 to 100, with higher scores indicating [REDACTED]. [REDACTED] total score will not be calculated when >5 items within the questionnaire are missing.

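### For what appears to be the same questionnaire, the SAP allows a total with up to 14 missing items where the protocol allows 5, and it lists no change from the protocol

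*SAP*

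**What the plan says.** Protocol 10.4.3 describes a disease-specific questionnaire (name redacted) and states that its "total score will not be calculated when >5 items within the questionnaire are missing". SAP 3.8.2 describes a questionnaire (name also redacted) and states that its "total score will not be calculated when >14 items within the questionnaire are missing".

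SAP 3.8.2 scores both the domains and the total as the sum of the answered item scores, divided by the sum of the maximum possible scores of those same items, times 100. Unanswered items drop out of numerator and denominator alike.

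SAP 3.7, headed "Changes to Analyses Planned in the Protocol", has a one-word entry: none. Protocol Section 13 and SAP Section 1 both give the SAP precedence over the protocol's statistical methods.

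**The concern.** Two documents in force together give different rules for when the same score exists. SAP version 1.1 says that it is based on protocol Amendment 4/4.1, the version under review, so this is not a remnant of superseded text.

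Because the SAP prevails, its looser limit would be the one programmed. The formula puts any partial form on the full 0 to 100 scale, so in a summary table a total from a heavily incomplete form looks the same as one from a complete form. The missing-item limit is the only stated safeguard on that total. The areas covered are diverse (sleep, eating, mental status, clothing and others), so unanswered items cannot simply be assumed to resemble answered ones.

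SAP 7.7.2 summarises change from baseline in questionnaire scores by cohort with 95% confidence intervals, and each cohort has about 12 subjects. At stake is which subjects contribute to those summaries and how much information lies behind each total. A reader who relied on SAP 3.7 would also wrongly conclude that the protocol's rule still applied.

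**Working it through.** **Step 1. Is it the same questionnaire?** The name is redacted in both places, so the match rests on the descriptions.

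| Feature | Protocol 10.4.3 | SAP 3.8.2 |
|---|---|---|
| Recall | "The recall period is 2 weeks" | "is a questionnaire for the last 2 weeks. It comprises" |
| Areas, after overall functioning | "sleep, itching/embarrassment, mental status, swelling/eating, and limits" (looks) | "sleep, itching/embarrassment, mental status, swelling/eating, and limits in look" |
| Total | "Total scores range from 0 to 100, with higher scores indicating" (rest redacted) | 0 to 100, higher is worse |
| No total if missing items exceed | 5 | 14 |

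The recall period, the six areas in the same order, and the range all agree. No other questionnaire described in either document has this content. The identification is very likely right, but it remains an inference.

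**Step 2. Which forms are treated differently?** With 0 to 5 missing items, both rules give a total. With 15 or more, neither does. With 6 to 14, the protocol sets the total to missing and the SAP calculates it. The tolerance rises by 14 − 5 = 9 items. This is the only magnitude that the documents give directly.

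**Step 3. How little can support a total?** Let N be the number of items and m the number missing. N is redacted, so I assume 15 to 40. At N = 15 the SAP limit would exclude only a wholly blank form, so 15 is the smallest count at which it does anything. The upper end of 40 is arbitrary. Items are taken as equally weighted, in line with the 0 to 4 scoring in protocol 10.4.3 (the item range is redacted in the SAP).

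- Minimum share answered = (N − m)/N, at m = 5 (protocol) and m = 14 (SAP).
- Part of the 0 to 100 total that the answered items leave undetermined = 100 × m/N points.

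| Assumed N | Answered, protocol | Answered, SAP | Undetermined, protocol | Undetermined, SAP |
|---|---|---|---|---|
| 15 | 10/15 = 66.7% | 1/15 = 6.7% | 33.3 | 93.3 |
| 20 | 15/20 = 75.0% | 6/20 = 30.0% | 25.0 | 70.0 |
| 25 | 20/25 = 80.0% | 11/25 = 44.0% | 20.0 | 56.0 |
| 30 | 25/30 = 83.3% | 16/30 = 53.3% | 16.7 | 46.7 |
| 40 | 35/40 = 87.5% | 26/40 = 65.0% | 12.5 | 35.0 |

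**Step 4. What could one such form do to a cohort mean?** With 12 contributing subjects (SAP 3.3), divide the undetermined points by 12. Under the SAP limit the bound runs from 93.3/12 = 7.8 points (N = 15) to 35.0/12 = 2.9 points (N = 40). Under the protocol limit it runs from 33.3/12 = 2.8 to 12.5/12 = 1.0. These are worst-case bounds for one form at the limit, with the baseline score held fixed. They are not expected errors.

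**Step 5. Is the entry in SAP 3.7 accurate?** On this limit it is not. The UCT offers a second check: protocol 10.4.2 withholds the UCT total when more than one item is missing, and SAP 3.8.1 when one or more is missing. So the entry does not hold for that scoring rule either.

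**The case against.** The strongest case on the other side has four parts.

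*The analysis can be run as written.* The precedence clauses settle which limit applies, and SAP 3.8.2 gives a full formula. That is true. But precedence only decides which rule is used. It neither discloses nor justifies the change.

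*SAP 3.7 concerns planned analyses.* The protocol's limit sits in its assessment section (10.4.3), not in Section 13. This softens the charge of non-disclosure. It does not remove it, because a scoring rule decides which subjects have a value to analyse.

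*The consequence is small.* Changes in questionnaire scores fall under the SAP's exploratory endpoints and analyses (5.3 and 7.7.2), no hypothesis is tested, and the primary endpoint is the UCT. This stands. Instrument names are redacted in 7.7.2 and some instruments are cohort-specific, so even the link to a particular summary is an inference.

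*The size depends on a redacted number.* This also stands. If there are 28 or more items, a form with 14 missing is still at least half answered (14/28 = 50%).

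A reader might go further and infer that mostly blank follow-up forms will be compared with complete baselines. The documents do not support that. The limit applies at every administration, baseline included, and nothing indicates how often forms will be this incomplete. A reader might also infer that only the SAP rule lets a whole domain go missing. Items per domain are not visible, and a domain of five or fewer items could be entirely absent under the protocol limit too.

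**Conclusion.** The point holds as an undisclosed inconsistency in a scoring rule, of minor consequence. The protocol tolerates 5 missing items and the SAP 14 for what appears to be one questionnaire, and SAP 3.7 reports no change. Totals with 6 to 14 missing items would be created and rescaled where the protocol would have none.

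The SAP rule is looser at every assumed item count, but how much it matters cannot be fixed from the documents. Over 15 to 40 items the floor on the share answered is about 7% to 65%, against 67% to 88% under the protocol. These figures rest on the assumed item count, equal item weights and the inferred identity of the instrument. They describe what the rule permits, not what the data will show.

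It might be tempting to read this as a threat to the trial's main result, or as proof that the SAP figure is a mistake. Neither follows. The UCT has its own missing-item rule, and nothing in the documents shows which of the two limits was intended.

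**What to change.** Reconcile the two limits. The default is to use the protocol's limit in SAP 3.8.2, so that no total is calculated when more than 5 items are missing. That changes one number, and its downside is possibly a few more missing totals.

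If 14 is intended, then:

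- justify it in SAP 3.8.2 against the questionnaire's item count;
- list it as a change in SAP 3.7;
- repeat the change-from-baseline summary with totals restricted to forms with at most 5 missing items, as a sensitivity check.

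That route costs a short justification and one repeated table. Either way, correct the entry in SAP 3.7, since the UCT missing-item rule also differs between the documents.

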3.8.7 Urticaria Patient Daily Diary

All patients were provided with a Urticaria Patient Daily Diary (UPDD) to complete daily. The UPDD has 3 separate versions; one for CholU patients (including itch, hives and elicitors) (Appendix B.1.1), one for UF patients (including redness, hives, and itch) (Appendix B.1.2), and one for CSU patients (including itch and hives) (Appendix B.1.3). Complete Response (CR) and Clinically Meaningful Response (CMR) are defined in Section 4.

3.8.8

[REDACTED] is a 7-day sum of [REDACTED] [REDACTED], where [REDACTED] [REDACTED] respectively, and [REDACTED] is the intensity of the [REDACTED] (Appendix B.1.1). The symptom score [REDACTED] ranges from [REDACTED]

[REDACTED] using the numeric rating scale (NRS). The [REDACTED] ranges from [REDACTED] and the values are as follows:

The 7-day sum is calculated as $7 \times$ (times) mean of all available daily [REDACTED] scores.

The [REDACTED] will be set to missing when no UAS scores are recorded for a given 7-day period. CR and CMR are defined in Section 4.

3.8.9 [REDACTED]

[REDACTED] is a 7 day sum of the daily [REDACTED] and the daily [REDACTED] score (Appendix B.1.3, Question 1).

The daily [REDACTED] score ranges from [REDACTED] on NRS. The possible range of the weekly CR and CMR are defined in Section 4.

The [REDACTED] score is calculated as $7 \times$ mean of all available daily [REDACTED] scores.

The [REDACTED] will be set to missing when no [REDACTED] scores are recorded for a given 7 day period. [REDACTED] and [REDACTED] Score

[REDACTED] are derived by adding up the daily [REDACTED] and [REDACTED] scores respectively (Appendix B.1.3, Question 1) for 7 days a week throughout the study. The [REDACTED] score ranges from [REDACTED] and the [REDACTED] score ranges from [REDACTED] using the numeric rating scale (NRS). The possible range of the weekly score is [REDACTED]. The [REDACTED] and the [REDACTED] score is calculated as $7 \times$ mean of all available daily [REDACTED] and [REDACTED] scores respectively.

Missing diary entries will be handled in the same way as described for the Weekly [REDACTED].

3.8.10 Additional Measures for Disease Activity and Functional Status

The following assessments will be administered to assess disease activity and functional status. The assessments will be cohort-specific.

- [REDACTED] (Appendix B.8) will be used to determine disease activity in subjects with recurrent [REDACTED], independent of its underlying causes. Subjects will use the [REDACTED] for daily documentation of [REDACTED] episodes including duration, severity and impact on daily functioning and appearance.

- The [REDACTED] and [REDACTED] scoring systems will be used to assess disease activity.

3.8.11 Skin Biopsies (optional and only in certain sites)

The assessments of the skin biopsies will include:

- Haematoxylin and eosin (H&E) and giemsa stains to assess the number of MCs and eosinophils in the skin
- Other potential post hoc analyses to investigate the mechanism of action of AK002

3.9 Safety Assessments

3.9.1 Physical Examination

Physical examinations will be conducted at Visits 1 to 7. Clinically significant findings will be reported as adverse events.

3.9.2 Vital Signs, Height and Weight

Vital signs are measured at all visits. It includes blood pressure (BP), body temperature, heart rate, and respiratory rate. Height (cm) and body weight (kg) are also measured at the same visits.

3.9.3 Laboratory Tests

Laboratory tests will be collected at all visits. The tests include hematology, chemistry and CBC with differential, and urinalysis panels. Laboratory values will be categorized according to the appropriate laboratory reference ranges.

3.9.4 Anti-Drug-Antibodies

Blood will be collected for the determination of anti-drug antibodies (ADA) before the first dose at Visit 2 and at all the following visits. An unscheduled blood sample for ADA may be obtained if a related adverse event suspected of being associated with immunogenicity occurs.

3.9.5 Electrocardiogram

Standard 12 lead electrocardiograms (ECGs) will be recorded at all visits.

3.9.6 Pregnancy Testing

Serum pregnancy test (post menopause FSH) will be done only at Baseline. Urine pregnancy (for all women of child-bearing potential) will be done at Visits 2 to 7.

3.9.7 Tolerability/Acceptability

Adverse events leading to study drug discontinuation will be collected.

3.9.8 Medical History and Adverse Events (AEs)

AEs that occur on/after signing Informed Consent Form (ICF) will be recorded on the AE CRF. Medical history and AEs will be coded for preferred term (PT) and system organ class (SOC) using Medical Dictionary for Regulatory Activities (MedDRA) version 21.0. AEs are evaluated by the investigators for seriousness, causality, and severity.

3.9.9 Prior, Concomitant, and Prohibited Medications

Prior medications and concomitant medications will be extracted from the Prior/Concomitant Medication CRF. Medications taken prior to Study Day 1 will be considered as prior medications and medications taken on or after Study Day 1 will be considered as concomitant medications. Prior and concomitant medications will be coded using WHO Drug Dictionary (WHODD March 2018 release) for Preferred Term (PT) and Anatomical Therapeutic Chemistry (ATC) classification.

Prohibited medications include, but are not limited to,

- Omalizumab
- H2-antihistamines
- Routine (daily or every other day during 5 or more consecutive days) doses of systemic corticosteroids
- Routine (daily or every other day during 5 or more consecutive days) doses of systemic hydroxychloroquine
- Routine (daily or every other day during 5 or more consecutive days) doses of methotrexate, cyclosporine A, cyclophosphamide, tacrolimus and mycophenolate mofetil
- Intravenous immunoglobulin G
- Plasmapheresis
- Regular (daily or every other day) doxepin (oral)
- Inactive vaccination
- Live attenuated vaccine
- Leukotriene Antagonists

4. Definitions

Table 4 Terminology and Definition

Terminology	Definition
Study Medication/Drug (SM)	AK002 administered by IV infusion.
Study Day	The first dose date (Day 1) is defined as the date on which a subject took the first dose of study medication (SM). Other study days are defined relative to Study Day 1. For visits prior to the first dose of the SM, Study Day is calculated as Visit Date – Day 1. For visits after the first dose, Study Day is calculated as Visit Date – Day 1 +1.
Enrolled	Subject who has signed informed consent, met all eligibility criteria at Screening, and having received the first dose of the study drug.
Completer for the Study	Subject who completes End of Study visit
Baseline	Baseline is defined as the non-missing value collected most recent to and before the time of the very first dose of the SM.
Prior Medication	Medication collected on the Prior/Concomitant Medication CRF, with start date prior to Study Day 1.
Concomitant Medication	Medication collected on the Prior/Concomitant Medication CRF, with end date on/after Study Day 1.
Treatment-emergent	Adverse events with onset date on or after the start of first study drug administration.
UCT Response (all CU subjects)	UCT score ranges from 0 to 16. CR is UCT score ≥ 12 AND an increase from baseline in UCT score of ≥ 3 points. CMR is an increase in UCT score of ≥ 3 points. DC is UCT score ≥ 12 . An increase from baseline in UCT score of ≥ 3 points is also regarded as the minimally clinically important difference.
UAS7 Response (CSU subjects)	Weekly UAS7 ranges from 0 to 42. [REDACTED]
[REDACTED] Response (CholU subjects)	Weekly [REDACTED] score ranges from 0 to 168. [REDACTED]

5. Efficacy and Safety Variables

5.1 Primary Endpoint

- 1) The primary efficacy endpoint is the change in Urticaria Control Test (UCT) for each population (CSU-XN, CSU-XF, UF, and CholU). The UCT is a score for symptom control in chronic urticaria, from Day 1 (baseline) to Week 10 for subjects enrolled under Protocol Amendment 2.1 and Week 22 for all remaining subjects (i.e., those on study during Protocol Amendment 3). A change of the UCT score of 3 or more points is regarded as clinically relevant (minimal clinically important difference [MCID]). If Week 10 or Week 22 measures

are not available, they will be imputed with last observation carried forward method (LOCF). The data summary will include Week 10 and Week 22 derived from the available data and Week 10/LOCF and Week 22/LOCF derived from the available plus the imputed data.

5.2 Secondary Endpoints

- 1) Proportion of subjects with CR, CMR, and DC based on UCT (all patients) at all time points. Section 4 provides the definition of CR, CMR, and DC.
- 2) Change from baseline in disease activity as assessed by UAS7 at each week in CSU patients. If Week 10 or Week 22 measures are not available, they will be imputed with the last non-missing weekly UAS7 (LOCF). The data summary will include Week 10 and Week 22 derived from the available data and Week 10/LOCF and Week 22/LOCF from the available plus the imputed data.

